7.6. Vital Signs

Analysis of vital signs will be based on on-treatment results, as described in Section 7.1. Measurements collected outside of the defined treatment periods will be excluded. All results will be included in the patient listings.

Summary statistics for vital signs will be presented at baseline and at each visit. Actual values and changes from baseline to each visit will be summarized. The incidence of potentially clinically significant vital signs will be summarized. Summaries of potentially clinically significant values will include all relevant post-baseline values (including scheduled, unscheduled, and early termination visits). A scatter plot will be provided for the baseline and the maximum on treatment value for weight.

Table 7 specifies the criteria for identifying vital signs as potentially clinically significant for adults and adolescents. In order to be identified as potentially clinically significant vital sign, the result would need to meet both identified conditions (ie, satisfies the specified criteria and results in a change from baseline of at least the magnitude specified). A listing for potentially clinically significant vital signs will be presented.

Table 7: Criteria for Potentially Clinically Significant Vital Signs

Vital Sign	Adults (≥ 18 years)		Adolescents (12 to < 18 Years)	
	Criterion value	Change from baseline	Criterion value	Change from baseline
Heart rate	>100 bpm	Increase of ≥ 30	>100 bpm	Increase of ≥ 30
	<50 bpm	Decrease of ≥ 30	<60 bpm	Decrease of ≥ 30
Systolic BP	>160 mmHg	Increase of ≥ 30	>130 mmHg	Increase of ≥ 30
	<90 mmHg	Decrease of ≥ 30	<90 mmHg	Decrease of ≥ 30
Diastolic BP	>100 mmHg	Increase of ≥ 12	>85 mmHg	Increase of ≥ 12
	<50 mmHg	Decrease of ≥ 12	<55 mmHg	Decrease of ≥ 12
Respiratory rate	>24 breaths/min	Increase of ≥ 10	>20 breaths/min	Increase of ≥ 10
	<6 breaths/min	Not applicable	<10 breaths/min	Not applicable
Temperature	$>100.5^{\circ}\text{F}$	Increase of ≥ 2	$>100.5^{\circ}\text{F}$	Increase of ≥ 2
	$<96.5^{\circ}\text{F}$	Not applicable	$<96.5^{\circ}\text{F}$	Not applicable

7.7. Electrocardiography

Analysis of ECG findings will be based on on-treatment results, as described in Section 7.1. Measurements collected outside of the defined treatment periods will be excluded. All results will be included in the patient listings.

Shifts (normal and abnormal) from baseline to week 52 and to overall will be summarized using patient counts. For overall, the worst post-baseline finding (eg, the abnormal finding if there are both normal and abnormal findings) for the patient will be summarized. Summary statistics for ECG variables will be presented at week 52. Actual values and changes from baseline to each

visit will be summarized. ECG results at weeks 24 and 36 will be presented in the patient listings.

The following categorical analyses represent the criteria for potentially clinically significant QTc results. Both QTc Bazett and Fridericia interval will be presented using descriptive statistics.

- Absolute value at week 52
 - QTc interval >450 msec
 - QTc interval >500 msec
- Change from baseline to week 52
 - QTc interval increase >30 msec
 - QTc interval increase >60 msec
- Combined absolute value and change from baseline to week 52
 - QTc interval >450 msec and QTc interval increase >30 msec
 - QTc interval >450 msec and QTc interval increase >60 msec
 - QTc interval >500 msec and QTc interval increase >30 msec
 - QTc interval >500 msec and QTc interval increase >60 msec

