### **3.16.5.    Unscheduled Visits**

An unscheduled visit may be performed at any time during the study at the patient’s request or as deemed necessary by the investigator. The date and reason for the unscheduled visit, as well as any other data obtained (eg, adverse events, concomitant medications and treatments, and results from procedures or tests), will be recorded on the CRF and noted within the patient’s source notes.

Procedures performed during unscheduled visits include the following:

- Perform vital signs measurements (includes systolic and diastolic blood pressure, pulse, body temperature, and respiratory rate).
- Perform adverse event inquiry.
- Perform concomitant medication inquiry.
- Perform study compliance review.

Other procedures may be performed at the discretion of the investigator. As outlined in Section 4.4, subjects who discontinue study treatment will have all visit 17 procedures performed at an unscheduled visit. This visit should be scheduled as soon as possible after the time of treatment discontinuation.

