#### **4.4.1. Discontinuation of Study Treatment**

If premature discontinuation of study treatment occurs for any reason, the patient should continue attending remaining study visits while off study treatment. The patient should not be considered withdrawn from the study due to interruption or discontinuation of study treatment. For this study, it is very important to continue collecting data from all patients whether or not they complete treatment.

If premature discontinuation of study treatment occurs, the patient should return to the clinic as soon as possible for a study treatment discontinuation visit. All evaluations should be performed as an unscheduled visit and include all the assessments specified in the protocol for the early withdrawal visit (see Table 2). The investigator must determine the reason for and the date of discontinuation of study treatment and record this information in both the source documentation and the Study Drug Treatment Completion CRF. The patient's continued participation in the study must be discussed by the investigator and site staff with the patient; the investigator and site staff must also request the patient to continue attending study visits according to the study visit schedule with all assessments completed up to week 52 (visit 17). The CAE event status and safety assessments at week 52 (visit 17) are the priority assessments for patients that prematurely discontinue study treatment. At a minimum, the investigator should make every effort to obtain information regarding serious adverse events, CAE events, and survival status at week 52. A safety follow-up visit (visit 18) should be conducted 12 weeks after visit 17.

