7. SAFETY ANALYSIS

7.1. General

The safety analysis set will be used for all safety analyses, unless otherwise noted. Summaries will be presented by treatment group actually received.

In this study, patients are encouraged to remain in the study and complete the remaining study assessments even after withdrawing from treatment. The assessment of safety in this context will be based on measurements and events recorded during the treatment period (on-treatment). On-treatment assessments will be defined as events and measurements occurring between the first dose of study drug and the end of treatment (week 52) visit for patients who complete treatment and between the first dose of study drug and the last dose of study drug + 4 weeks for patients who discontinued treatment early.

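### SAP 7.7 counts QTc values above the preset limits at week 52 only, which is narrower than protocol 9.7.2 and is not declared in SAP section 10

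*SAP*

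**What the plan says.** **Protocol**

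- Table 2 and sections 7.5 and 9.7.1 schedule ECGs at screening and at weeks 24, 36, and 52 or early withdrawal. Section 7.5 leaves the limits for potentially clinically significant ECG values to the SAP. It does not restrict the visits to which those limits apply.
- Section 9.7.2 treats laboratory, ECG and vital-sign data together. All values are to be compared with preset limits, and those beyond them listed and summarized.
- Section 4.4.1, on patients who stop treatment: "All evaluations should be performed as an unscheduled visit and include all the assessments specified in the protocol for the early withdrawal visit". Section 3.16.5 repeats this: "subjects who discontinue study treatment will have all visit 17 procedures performed at an unscheduled visit".

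**SAP**

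- Section 7.7 has three QTc threshold blocks. The first is headed "Absolute value at week 52" (above 450 and 500 msec). The second is change to week 52 (above 30 and 60 msec), and the third combines the two, also at week 52.
- Section 7.7 places the summary statistics at week 52, then adds: "Actual values and changes from baseline to each" visit will be summarized. The next sentence reads: "ECG results at weeks 24 and 36 will be presented in the patient" listings.
- The normal/abnormal shift has an overall row: "For overall, the worst post-baseline finding" is taken for each patient.
- Section 7.7 adds "Measurements collected outside of the defined treatment periods will be excluded". Section 7.1 ends the on-treatment period at "the last dose of study drug + 4 weeks for patients who discontinued treatment early".
- Sections 7.5 and 7.6 count potentially clinically significant laboratory values and vital signs over all relevant post-baseline values, with unscheduled and early termination visits included.
- Section 10 reports no changes to the analyses in protocol Amendment 04.

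**The concern.** The protocol's rule covers every ECG value, while the SAP's threshold table covers one visit. A QTc above the limits at week 24, week 36 or a treatment-discontinuation visit would not clearly be counted by treatment group, and section 10 does not tell the reader that the rule has been narrowed. A programmer also cannot follow all the sentences of section 7.7 at once: summaries to each visit, statistics at week 52, and weeks 24 and 36 in listings. What is at stake is the only planned between-group count of patients beyond the prespecified QTc limits.

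**Working it through.** There is no plan figure to reproduce. The check compares the texts and adds some schedule arithmetic.

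**1. Coverage.** There are three scheduled post-baseline ECGs (weeks 24, 36, 52), and the threshold blocks use one. With 450 planned patients and full retention, 3 × 450 = 1350 ECGs are scheduled. Of these, 450 enter the QTc counts and 2 × 450 = 900 do not.

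**2. Is the narrowing permitted, and is it declared?** It is permitted. The opening of protocol section 9 and section 9.12 let the SAP describe changes, and the SAP preface says that the SAP prevails and discrepancies are explained in the study report. It is not declared. Section 10 says that there are no changes, and its Tables 8 and 9 record no week 52 restriction for QTc.

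**3. Patients who stop treatment and stay in the study.** Inputs: doses every 4 weeks from week 0 to week 48, visit windows of 7 days either way, and on-treatment ending at last dose + 4 weeks.

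- Latest case, last dose at the week 44 visit: 44 + 1 (window) + 4 = week 49. The earliest week 52 visit is 52 − 1 = week 51. Since 49 < 51, the week 52 ECG is off treatment and excluded.
- With a last dose at the week 24 visit or later, the week 24 ECG is on treatment. With a last dose at week 36 or later, so is the week 36 ECG. A last dose at week 32 is borderline for week 36 (32 + 4 = 36).
- So a last dose at week 24, 28, 32, 36, 40 or 44 leaves at least one on-treatment scheduled ECG outside the QTc table and no scheduled ECG inside it.

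**4. Where the treatment-discontinuation ECG goes.** It is recorded as an unscheduled visit. SAP 4.5 brings unscheduled assessments into the by-visit safety summaries, but does not say to which visit this one belongs. The SAP 4.5 rule that moves an early termination assessment to the next scheduled visit is for efficacy only. SAP 4.5 also defines a safety endpoint (last on-treatment observation), but section 7.7 does not use it. For patients who leave the study, visit 17 is labelled end of treatment or early withdrawal, so placing their ECG there is the natural reading. The gap is therefore mainly for those who stop treatment and stay.

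**5. Can the missed outliers be sized?** No. The documents give no exceedance rate, no within-patient correlation and no discontinuation rate. As an illustration, assume an exceedance probability p = 1% at each visit:

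- Independent visits: P(any of three) = 1 − 0.99³ = 2.97%. Week 52 alone finds 1/2.97 = 33.7% of these patients and leaves out 66.3%.
- Full persistence within a patient: week 52 finds them all and leaves out 0%.

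A range of 0% to 66% that rests wholly on assumptions is not an estimate.

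**The case against.** The best case for the plan has four parts.

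- **The restriction is openly written.** Protocol 7.5 delegates the ECG criteria to the SAP, and the SAP is allowed to prevail. This stands, so there is no breach of authority. It does not make the statement of no changes in section 10 correct.
- **Weeks 24 and 36 are not lost.** All results are listed and the worst normal/abnormal finding is counted. An ECG change that the investigator judges clinically significant becomes an adverse event (protocol 7.5), and adverse events are tabulated by group. If the each-visit sentence governs, by-visit statistics would include the maximum (SAP 4.1), which shows whether any QTc in a group passed a limit. This stands and limits the harm. None of it gives a count of patients beyond the limits by group.
- **The three ECGs sample similar exposure.** Each is taken before dosing, or 4 weeks after the final dose. With a terminal half-life of about 26 days (protocol 1.3.2.1), week 24 is 168/26 = 6.5 half-lives after the first dose. This stands: weeks 24 and 36 add repeat observations more than a new exposure condition.
- **Earlier data are reassuring.** Protocol 1.3.2.2 reports no clinically meaningful ECG changes in completed studies. This stands, although protocol 1.4.1 says that subcutaneous safety data are limited.

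Three stronger readings are tempting, and the documents do not support them. A reader might infer that section 7.7 breaks the SAP's own rule for laboratory values and vital signs. Sections 7.5 and 7.6 are written for those data only and do not bind ECG; they show the approach used elsewhere. A reader might infer that about two thirds of patients with an outlier will be missed, but that needs independent visits within a patient, which nothing in the documents supports. A reader might also infer that the treatment-discontinuation ECG is shut out of the summaries. SAP 4.5 admits unscheduled assessments, and only their visit assignment is unstated.

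**Conclusion.** The point holds and its effect is modest. SAP 7.7 counts QTc exceedances at one of three scheduled post-baseline ECGs, protocol 9.7.2 promises all values, and section 10 declares no change. Section 7.7 also contradicts itself on what is summarized at weeks 24 and 36. These conclusions rest on the text alone.

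The finding for patients with a last dose at weeks 24 to 44 who stay in the study rests on the dosing schedule, the visit windows and the on-treatment definition. How many such patients there will be, and how many outliers would go uncounted, cannot be derived from the documents. The table is descriptive and no hypothesis test depends on it. The point is worth correcting because it concerns safety detection, the data are already collected, and the correction is cheap.

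**What to change.** In SAP 7.7:

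1. Count QTc outliers (absolute, change and combined) on any on-treatment post-baseline ECG: scheduled, unscheduled or early termination. State that the treatment-discontinuation ECG is included if it falls within last dose + 4 weeks.
2. Show by-visit rows for weeks 24, 36 and 52 beside that count.
3. Reconcile the each-visit sentence with the week 52 and listing sentences.
4. If the week 52 restriction is kept instead, declare it in section 10.

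The cost is SAP wording and one table program; no new data are needed. The downside is that a worst-value count picks up more isolated outliers in both groups, and patients with more unscheduled ECGs have more chances to be counted. The by-visit rows let the reader judge this.

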7.8. Physical Examinations

Analysis of physical exam findings will be based on on-treatment results, as described in Section 7.1. Measurements collected outside of the defined treatment periods will be excluded. All results will be included in the patient listings.

Shifts (normal and abnormal) from baseline to each visit will be summarized using patient counts and percentages for each category. Descriptive statistics for weight will be provided.

7.9. Other Safety Measures and Variables

7.9.1. Concomitant Therapy or Medication

All concomitant medications will be coded using the WHO Drug. The incidence of concomitant medications will be summarized by therapeutic class and preferred term. Patients are only counted once in each therapeutic class and once in each preferred term.

Concomitant medications include all medications taken during the treatment period. Medications with a start date greater than the upper bound of the treatment period will be considered post-treatment. Medications will be categorized in every period (prior, concomitant, post-treatment) in which it was taken. If the medication start/stop date is missing or partial, the medication will be considered concomitant unless there is evidence to the contrary (eg, month and year of stop date is present and is less than the month and year of the first dose of study drug).

8. PHARMACOKINETIC/PHARMACODYNAMIC ANALYSIS

The safety analysis set will be used for the following analyses, unless otherwise noted.

8.1. Pharmacokinetic Analysis

The PK endpoints are the serum reslizumab concentrations at baseline/DoR; weeks 1 (patients in US study centers only), 2, and prior to study drug administration at weeks 4, 8, 12, 16, 20, 32, 48, 52 or early withdrawal; and the follow up visit (approximately week 64). An additional PK sample will be collected 28 weeks (± 2 weeks) after the last dose of study drug (approximately week 76) for validation of the ADA assessment.

Reslizumab concentration data will be summarized descriptively for reslizumab-treated patients by time point. Reslizumab concentration data will additionally be summarized by ADA status. Samples from placebo-treated patients will not be analyzed. Listings for reslizumab concentration data will be presented.

The data will be pooled with data from other studies and analyzed using population PK and PK/PD analysis and reported in a separate report.

8.2. Pharmacodynamic Analysis

8.2.1. Target Biomarker (Blood Eosinophil Counts)

The target biomarker endpoints are the blood eosinophil counts at baseline/DoR; weeks 2, 4, 8, 12, 16, 32, 52 or early withdrawal; and the follow-up visit (approximately week 64).

Summary statistics of actual values, change from baseline, and percent change from baseline to each scheduled visit will be provided by treatment group, using the ITT analysis set. A line graph will be provided summarizing the mean blood eosinophil counts at each visit.

Blood eosinophils will additionally be examined for selected subgroups defined in Section 3.4. As described above, the analysis of eosinophils by subgroups will be summarized descriptively.

8.3. Immunogenicity

Samples for immunogenicity assessment for development of anti-drug antibodies will be obtained before the administration of study drug at DoR; prior to study drug administration at weeks 4, 16, 32, 52 or early withdrawal; and the follow-up visit (approximately week 64). Additional samples will be collected at the late follow-up visit (approximately week 76). These data may be presented in a CSR addendum.

Two types of antibody assay will be performed, an immunogenicity status assay (ADA) and neutralizing assay (NAb). For the ADA assay, a screening assessment will be performed which produces a positive or negative result. For samples with a positive result, a neutralizing assay will be performed, which also produces a positive or negative result; a titre value will be obtained to quantify the degree of binding.

A patient will be classified as having a treatment-emergent ADA response if a sample tested positive at any of the post-baseline time points but not at the baseline time point, or if the post-baseline ADA titer increased ≥ 4 -fold from a positive baseline ADA sample ([Shankar et al 2014](#)).

Anti-reslizumab antibody data, including neutralizing antibody and titer results for patients who have tested ADA positive, will be listed. The number of patients with positive/negative results will be summarized at each scheduled visit. Samples from placebo-treated patients will not be analyzed.

9. STATISTICAL SOFTWARE

All data listings, summaries, and statistical analyses will be generated using SAS[®].

10. CHANGES TO PROTOCOL-SPECIFIED ANALYSES

There are no changes to the analyses specified in the CSP, Amendment 04 to report.

- [Table 8](#) summarizes the key changes that have been implemented since the original approved SAP.
- [Table 9](#) summarizes the key changes that have been implemented since the approved SAP, Amendment 01.

Only substantive changes have been included; editorial and/or administrative changes are generally not listed.

Table 8: Key Changes to the Statistical Analysis Plan, Amendment 01

SAP Section	SAP Description	Change	Rationale
3.2	<<null>>	Patients dosed in error, but who otherwise received at least 1 dose of reslizumab, will be assigned to reslizumab for the analysis of safety data.	Clarified how safety analyses would be handled if a patient receives a combination of both treatments.
3.3.1 (Table 2)	<<null>>	
 • Patient was not on an ICS at baseline (at least a medium total daily dose) • Patients who received the incorrect study treatment at any point during the study 	Two additional protocol violations.
3.4.1	The primary efficacy endpoint will be analyzed separately for patients aged 12 to <18 years and ≥18 years.	Selected efficacy endpoints including CAEs (primary), pre-bronchodilator FEV₁, and blood eosinophils will be analyzed separately for patients aged 12 to <18 years and ≥18 years.	Subgroup analyses planned for FEV ₁ and eosinophils, in addition to CAE. Note: The same changes are applied to other subsequent subgroup sections (ie, 3.4.2, 3.4.5)
3.4.3	[Redacted content]		
3.4.4	<<null>>	Asthma Background Medication	Created new section for subgroups based on the identified classes of background asthma medication.
3.4.5	
 • Age group (<65, ≥65 years) • Race (White, Black, Asian, Other) • Region (US, non-US) • <<null>> 	
 • <<deleted>> • Race (White, Black, Asian, Other; Black, non-Black) • Region (North America, Europe, Latin America, Asia/Pacific; US, non-US) • ADA status (Positive, Negative) – for reslizumab-treated patients only 	Modifications to the race and region subgroups; removed additional subgroup category for age; included subgroup for ADA status.
4.2.4	The baseline value for blood eosinophil levels will be screening value (for	The baseline value for blood eosinophil levels will be the maximum value of the observed	Modified definition of baseline to potentially account for patients who fulfilled the eosinophil

SAP Section	SAP Description	Change	Rationale
	consistency with study entry criteria).	assessments from the screening visit to baseline/DoR (inclusive).	threshold prior to randomization, but not at the screening visit.
5.3	The baseline stratification factors (age and baseline blood eosinophil counts) will also be summarized. <<null>>	The baseline stratification factors (age and baseline blood eosinophil counts) and patients taking the various classes of background medication at baseline (defined in Section 3.4.4) will also be summarized. Age will be calculated based on the date of birth relative to the screening visit (date of informed consent). If regional data regulations prohibit collection of a full date of birth, then the patient’s age should be recorded on the CRF, if possible. If only a year of birth has been collected (and age has not otherwise been reported) then the missing date of birth will be imputed as 30 June (30 June YYYY) in order to derive the patient’s age at baseline.	Additional summaries based on the asthma medication classes. Clarification, since derivation of age may not always be possible due to partial birth dates.
5.5	<<null>>	In addition, the total daily ICS dose taken at baseline will be summarized descriptively. The reported ICS doses will first be converted to fluticasone equivalents using the following conversion factors.	Additional summary based on ICS dose at baseline; included Table 4 for ICS conversion factors.
6.2.2	Any clinical asthma exacerbations that occur between the completion of the first dose of study drug and 2 weeks after the end of treatment/early withdrawal visit will be counted towards the CAEs for analysis.	Any clinical asthma exacerbations that occur between the day of randomization and 2 weeks after the end of treatment/early withdrawal visit will be counted towards the CAEs for analysis.	Clarified that the lower bound of treatment period will be the day of randomization (rather than first dose date), in the case that the day of randomization and first dose date do not coincide. Note: The same changes are applied to other sections (ie, 4.5, 6.2.3, 6.2.6, 6.3)
6.2.3	The primary analysis based on the per protocol analysis set.	Per protocol analysis: on-treatment analysis of the primary endpoint based on the per protocol analysis set.	Clarified that the per protocol analysis is based on on-treatment events.
6.2.6	Time-to-first event will be analysed separately for all exacerbation events and on-treatment events.	Time-to-first event will be analysed for on-treatment events.	Time-to-first event only planned to be summarized for on-treatment events.

SAP Section	SAP Description	Change	Rationale
	
The time period for the primary time-to-event analysis will extend from the first dose of study drug to the end of treatment/early withdrawal visit (+2 weeks). Patients without an event during this time frame will be censored at the date of the end of treatment/early withdrawal visit (+2 weeks).
 
For the on-treatment analysis, only events occurring during the treatment period will be counted. Patients without an event during this time frame will be censored at either the date of the end of treatment (week 52) visit for patients who completed treatment and at the date of last dose (+4 weeks) for patients who discontinued early.
	
<<deleted>>
 
The time period for the on-treatment analysis will extend from the day of randomization to the cessation of study treatment, defined as the date of the end of treatment (week 52) visit for patients who completed treatment and the date of last dose (+4 weeks) for patients who discontinued treatment early. Patients without an event during the treatment period will be censored at either the date of the end of treatment (week 52) visit for patients who completed treatment or at the date of last dose (+4 weeks) for patients who discontinued early.
	
6.3.3.2	
Summary statistics of actual values and change from baseline to each scheduled visit and to endpoint will be provided by treatment group.
 
Analysis of the overall change from baseline over 52 weeks, and to each scheduled visit will be performed using a mixed effect model for repeated measures (MMRM) including fixed effects for treatment, visit, treatment by visit interaction, age group (12 to <18 years and ≥18 years), blood eosinophil counts at enrollment (300 to <400/μL and ≥400/μL), baseline value as a covariate, and patient as a random effect.
	
Summary statistics of actual values and change from baseline to each scheduled visit will be provided by treatment group.
 
Analysis of the change from baseline to each scheduled visit will be performed using a mixed effect model for repeated measures (MMRM) including fixed effects for treatment, visit, treatment by visit interaction, age group (12 to <18 years and ≥18 years), blood eosinophil counts at enrollment (300 to <400/μL and ≥400/μL), and sex, height and baseline value as
	
Summaries at endpoint have been removed.
 
Sex and height have been included as additional factors in the model for pulmonary function tests. Analysis of the overall change over 52 weeks has been removed.

SAP Section	SAP Description	Change	Rationale
	
Analysis of change from baseline to endpoint will be performed using an analysis of covariance (ANCOVA) model ... Based on the ANCOVA model ... with the corresponding p-value.
 
<<null>>
	
covariates, and patient as a random effect.
 
<<deleted>>
 
Model results will only be reported if there are at least 15 patients contributing to the analysis in each treatment group; otherwise only descriptive statistics will be displayed.
	
ANCOVA analysis at endpoint has been removed.
 
Pre-specified the approach to analysis in the case of small sample sizes (eg, in subgroups). Analyses based on less than 15 patients may result in convergence issues or general issues with interpretability.
 
Note: The same changes are applied to other subsequent efficacy sections (ie, 6.3.4.2, 6.3.5.2, 6.3.6.2, 6.3.7.2, 6.3.8.2, 6.3.9.2).

6.3.4.2	
A stratified (based on randomization strata) Cochran-Mantel-Haenszel (CMH) test will be used to analyze the proportion of patients achieving an increase of ≥ 0.5 in the AQLQ +12 score from baseline to each scheduled visit and endpoint.
	
The proportion of patients achieving an increase of ≥ 0.5 in the AQLQ +12 score from baseline to each scheduled visit will be summarized. A stratified (based on randomization strata) Cochran-Mantel-Haenszel (CMH) test will be used to analyze the proportion of patients achieving an increase of ≥ 0.5 in the AQLQ +12 score from baseline to Week 52.
	
Clarified that the planned analysis (CMH) will be done at Week 52; the rest of the visits will be summarized descriptively.
 
Note: The same changes are applied to other subsequent efficacy sections (ie, 6.3.5.2, 6.3.6.2, 6.3.8.2).

6.3.8.1			
6.3.8.2			

Table 8: Key Changes to the Statistical Analysis Plan, Amendment 01 (Continued)

SAP Section	SAP Description	Change	Rationale
7.3	<<null>>	In addition, adverse events that begin within 24 hours after study drug injection and injection-site adverse events (as recorded on the CRF) will each be summarized separately. Summaries for the most common adverse events (incidence ≥2% in reslizumab-treated patients) and adverse events occurring with greater frequency for reslizumab-treated patients compared to placebo will also be presented.	Additional AE tables.
7.3.1	<<null>>	Adverse events of special interest updated to include: 
 • Administration Site Reactions • Anaphylaxis and Hypersensitivity • Malignancies • Helminth Infections • Muscle Disorders/CPK 	Categories of adverse events have been added, along with the derivations of each.
7.3.2	<<null>>	Adverse events by subgroup	Created separate section for subgroup analysis and clarified the analyses.
7.5	Summary statistics for laboratory tests will be presented at baseline, at each scheduled visit and endpoint . Actual values and changes from baseline to each visit and endpoint will be summarized.	Summary statistics for laboratory tests will be presented at baseline and at each scheduled visit. Actual values and changes from baseline to each visit will be summarized. Shifts (below, within, and above the normal range) from baseline to	Summaries at endpoint have been removed. Note: The same changes are applied to other subsequent safety sections (ie, 7.6, 7.7, 7.8).

SAP Section	SAP Description	Change	Rationale
	
Shifts (below, within, and above the normal range) from baseline to each visit and endpoint will be summarized using patient counts and percentages.
 
Shift tables of abnormal values (change from baseline: high/normal to low, low/normal to high, and other) will be provided for creatine phosphokinase (CPK) at each visit and endpoint. Shifts from baseline (Grades 0 to 4) to each visit and endpoint will also be summarized for CPK.
	
each visit will be summarized using patient counts and percentages.
 
Shifts from baseline (Grade 0-4) will be provided for creatine phosphokinase (CPK) at each visit.
	
Additional shift table has been removed.

7.5	
<<null>>
 
Scatter plots of the maximum on treatment values for total bilirubin vs. alanine aminotransferase and for total bilirubin vs. aspartate aminotransferase (each presented as multiples of the ULN) will be provided.
 
Table 4 and Table 5
 
Grade 0: $\leq 1 \times \text{ULN}$ Grade 1: $>1 \times \text{ULN}$ to $\leq 2.5 \times \text{ULN}$ Grade 2: $>2.5 \times \text{ULN}$ to $\leq 5 \times \text{ULN}$ Grade 3: $>5 \times \text{ULN}$ to $\leq 10 \times \text{ULN}$ Grade 4: $>10 \times \text{ULN}$
 
$\geq 1.0 \times 10^9/\text{L}$
	
A post-baseline laboratory value will be considered potentially clinically significant only if it satisfies the specified criteria and is more extreme (farther from the limit) than the baseline value.
 
<<deleted>>
 
Combined into one table (Table 4).
 
Grade 0: $\leq 1.25 \times \text{ULN}$ Grade 1: $1.25 \times \text{ULN}$ to $1.5 \times \text{ULN}$ Grade 2: $1.6 \times \text{ULN}$ to $3 \times \text{ULN}$ Grade 3: $3.1 \times \text{ULN}$ to $10 \times \text{ULN}$ Grade 4: $>10 \times \text{ULN}$
 
$\geq 1.5 \times 10^9/\text{L}$
	
Modified the definition of potentially clinically significant values to account for presence of abnormal results at baseline.
 
Formal plots are not planned.
 
Combined for ease of review.
 
Updated the CPK toxicity grade classifications.
 
Updated the PCS value for eosinophils.

Table 8: Key Changes to the Statistical Analysis Plan, Amendment 01 (Continued)

SAP Section	SAP Description	Change	Rationale
7.6	<<null>> Table 6 and Table 7	Summaries of potentially clinically significant values will include all post-baseline values (including scheduled, unscheduled, and early termination visits). Combined into one table (Table 5).	Clarification Combined for ease of review.
8.2.1	Summary statistics of actual values and change from baseline to each scheduled visit and to endpoint will be provided by treatment group. Analysis of the overall change from baseline over 52 weeks and the change from baseline to each scheduled visit will use the MMRM model described in Section 6.3.3.2 with the exception of inclusion of sex and height in the model. Analysis of the change from baseline to endpoint will be performed using the ANCOVA model described in Section 6.3.3.2 with the exception of inclusion of sex and height in the model.	Summary statistics of actual values, change from baseline, and percent change from baseline to each scheduled visit will be provided by treatment group, using the ITT analysis set. <<deleted>>	Clarified that analysis of eosinophils will be based on the ITT analysis set. Included summary of percent change from baseline and removed summaries at endpoint. Eosinophils will be summarized descriptively.
8.2.3	The number of patients with positive or negative phadiatop results will be summarized at baseline and week 52.	<<deleted>>	Phadiatop allergy test is considered a baseline patient characteristic and will be summarized only at baseline.
8.3	<<null>>	Two types of antibody assay will be performed, an immunogenicity status assay (ADA) and neutralizing assay (NAb). For the ADA assay, a screening assessment will	Clarified the process for ADA samples.

SAP Section	SAP Description	Change	Rationale
		
be performed which produces a positive or negative result. For samples with a positive result, a neutralizing assay will be performed, which also produces a positive or negative result and a titre value will be obtained to quantify the degree of binding.
 
A patient will be classified as having a treatment-emergent ADA response if a sample tested positive at any of the post-baseline time points but not at the baseline time point, or if the post-baseline ADA titer increased \geq4-fold from a positive baseline ADA sample (Shankar et al 2014).
	

Table 9: Key Changes to the Statistical Analysis Plan, Amendment 02

SAP Section	SAP Description	Change	Rationale
2.1	A total of 400 patients are planned to be randomized in a 1:1 ratio (approximately 200 patients within each treatment group) to receive reslizumab 110 mg or matching placebo every 4 weeks for 52 weeks.	A total of 450 patients are planned to be randomized in a 1:1 ratio (approximately 225 patients within each treatment group) to receive reslizumab 110 mg or matching placebo every 4 weeks for 52 weeks.	Sample size aligned with amended protocol
2.3	Based on the assumptions above, 200 patients per group (400 total) will provide more than 90% power (99.6%) to detect significant treatment effect of reslizumab over placebo in the reduction of exacerbation rate. The sample size was increased beyond the sample size required to provide 90% power in order to allow sufficient number of patients to assess safety and immunogenicity. The current sample size also provides higher power for other efficacy endpoints.	Based on the assumptions above, 225 patients per group (450 total) will provide >90 % power to detect significant treatment effect of reslizumab over placebo in the reduction of exacerbation rate. The sample size was increased beyond the sample size required to provide 90% power in order to allow sufficient number of patients to assess safety and immunogenicity and to ensure adequate enrollment in the adolescent subset . The current sample size also provides higher power for other efficacy endpoints.	Sample size aligned with amended protocol
2.4	Patients who meet all inclusion criteria and none of the exclusion criteria will be randomly assigned to receive reslizumab 110 mg sc or matching placebo (approximately 200 patients per treatment group) in a 1:1 ratio.	Patients who meet all inclusion criteria and none of the exclusion criteria will be randomly assigned to receive reslizumab 110 mg sc or matching placebo (approximately 225 patients per treatment group) in a 1:1 ratio.	Sample size aligned with amended protocol
3	<<null>>	Site [REDACTED] was terminated due to numerous unresolved Good Clinical Practice (GCP) issues including an overall lack of adequate source documentation (letter to FDA dated 2 December 2016). The data from this site are deemed invalid and patients from this site will be excluded from the efficacy analysis but will be included as part of the safety analysis. In addition, these patents will be summarized as randomized, but not analyzed, as part of the	Termination of Site [REDACTED]
